8.8 Multiplicity

Since there are no formal hypothesis tests in this study, no adjustment will be made for multiplicity.

8.9 Sample Size and Power Calculations

For the adult stage of the study, a total of 80 subjects will be randomized to one of four vaccination groups in order to evaluate the safety of a single vaccination of V114.

For the infant stage of the study, approximately 250 subjects will be enrolled, with approximately 50 subjects in each of the five vaccination arms. The probability of detecting a lower response (as measured by the GMC) for a given serotype between 2 vaccination groups depends on the variability of the natural log antibody concentrations and the true difference between the groups. In [Table 7](#), the powers for detecting a lower response for various standard deviation estimates and true fold difference are displayed assuming 45 evaluable subjects per group (90% evaluability) and a one-sided alpha of 0.05. Given the standard deviation of the natural log antibody concentrations at PD3 is 1.0 and the true fold difference is 2-fold lower between any two vaccination groups, there is >90% (94.7%) power to detect a lower response (as measured by the GMC) in V114 for a given serotype.

Table 7 Power for Detecting a Lower Response for Varying Standard Deviation and True Differences with 45 Evaluable Subjects

SD of natural log concentrations [†]	True Fold-Difference Between Groups for a Given Serotype		
	1.5	2.0	2.5
0.8	77.1%	99.3%	>99%
1.0	60.4%	94.7%	99.6%
1.2	47.8%	85.9%	97.4%
1.4	38.9%	75.3%	92.4%

[†]The standard deviation (SD) estimates are representative of those observed in V114-003.

The widths of the 95% CIs for the serotype-specific GMCs depend on the sample size, variability of the natural log concentrations, and the magnitude of the GMC. It is assumed that 90% (45 subjects) of the subjects in each group will have evaluable immunogenicity results at 1 month PD3. In [Table 8](#), the 95% CIs for various hypothetical GMCs and standard deviation estimates for the natural log concentrations are displayed.

Table 8 95% CIs for Varying Standard Deviation and GMC Values with 45 Evaluable Subjects

SD of natural log concentrations [†]	Serotype-specific GMC [†]		
	1.0	2.0	3.0
0.8	(0.79, 1.27)	(1.57, 2.54)	(2.36, 3.81)
1.0	(0.74, 1.35)	(1.48, 2.70)	(2.22, 4.05)
1.2	(0.70, 1.43)	(1.39, 2.87)	(2.09, 4.30)
1.4	(0.66, 1.52)	(1.31, 3.05)	(1.97, 4.57)

[†]The standard deviation (SD) and GMC estimates are representative of those observed in V114-003.

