Statistical Methods for Key Immunogenicity Analyses	For the infant cohort, GMCs at PD3 along with two-sided 95% CIs will be computed for the 15 serotypes in V114 and 13 serotypes in Prevnar 13™. Additionally, GMC ratios (V114/Prevnar 13™) along with two-sided 95% CIs will be computed for the 13 serotypes in common between V114 and Prevnar 13™ for each V114 vaccination arm with Prevnar 13™. The CI for the ratio will be calculated using a 2-sample t-test approach based on the natural logarithm of the ratio.

Statistical Methods for Key Safety Analyses	For the adult cohort, within group summaries of safety (incidence rates and 95% CIs) will be provided for each V114 arm following a single dose. For the infant cohort, comparisons will be made between the V114 arms and Prevnar 13™ following each dose and across all doses. The analysis of safety results for the infant cohort will follow a tiered approach (Tier 1 through Tier 3). The Tier 1 safety endpoints in this study consist of the solicited injection-site (redness, swelling, and pain/tenderness) and solicited systemic (irritability, drowsiness, hives/welts, and appetite lost) AEs from the infant cohort and will be subject to inferential testing for statistical significance with p-values and 95% confidence intervals provided for between-group comparisons (V114 versus Prevnar 13™). Tier 2 parameters will be assessed via point estimates with 95% confidence intervals provided for between-group (V114 versus Prevnar 13™) comparisons; only point estimates by treatment group are provided for Tier 3 safety parameters. These analyses will be performed using the Miettinen and Nurminen method, an unconditional, asymptotic method.

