Interim Analyses	Two interim analyses will be conducted during this study: (1) A first interim analysis will be performed when ~100% of the vaccinated subjects in the adult cohort and small infant cohort have completed postvaccination safety follow-up (single dose for adult cohort and postdose 3 for the small infant cohort) and ~100% of the immunogenicity results of IgG responses adult (postvaccination) and small cohort infant (postdose3) immunogenicity results of IgG responses are available; (2) A second interim analysis will be performed in this study when ~100% of PD3 immunogenicity results for all infants in Stage 2 (small and large cohorts) are available. An internal statistician and statistical programmer assigned to the protocol will be unblinded throughout the duration of the study to facilitate the performing of the interim analysis as well as creation of the eDMC safety reports for ongoing safety review. Results of the interim analysis will be provided and reviewed by the eDMC, and group summaries will be reviewed by the Sponsor's study team. The Sponsor's study team (except for the MRL statistician and programmer) will be blinded to the V114 formulation at the subject level. The Sponsor's study team will use the results to make scientific decisions regarding future studies. It may also inform certain scientific consultations.
Multiplicity	No multiplicity adjustment is planned since there are no formal hypothesis tests in this study.
Sample Size and Power	For the infant stage of the study, approximately 250 subjects will be enrolled, with approximately 50 subjects in each of the five vaccination arms. Assuming 90% evaluability at PD3 (~45 subjects per group), a standard deviation of the natural log antibody concentrations at PD3 of 1.0, and a one-sided alpha of 0.05, there is >90% power to detect a lower response (as measured by the GMC) in V114 for a given serotype if the true fold difference is 2-fold lower between any two vaccination groups.

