8.3 Hypotheses/Estimation

Objectives of the study are stated in Section 3.0. This is an estimation study and no formal hypothesis testing will be performed.

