8.6 Statistical Methods

8.6.1 Statistical Methods for Efficacy Analyses

This section describes the statistical methods that address the primary and secondary objectives. Methods related to exploratory objectives will be described in the supplemental SAP.

Analysis of the immunogenicity data from the infant stage of the study will be based on the combined data from Stage 2 Part I and Stage 2 Part II.

To address the primary infant immunogenicity objective #2, GMCs at 1 month PD3 along with two-sided 95% CIs will be computed for the 15 serotypes in V114 for V114 medium, V114 high, and 13 serotypes in Prevnar 13TM. Point estimates of GMCs are the exponentiated estimates of the mean log_e concentrations. The confidence intervals for GMCs are the exponentiated confidence intervals for the mean log_e concentrations, based on 1-sample t-distributions. Additionally, GMC ratios (V114/Prevnar 13TM) along with two-sided 95% CIs will be computed for each of V114 medium and V114 high relative to Prevnar 13TM for the 13 common serotypes. The CI for the ratio will be calculated using a 2-sample t-test approach based on the natural logarithm of the ratio.

To address the secondary infant immunogenicity objective #1, the proportion of subjects achieving the serotype-specific threshold value of $\geq 0.35\mu\text{g}/\text{mL}$ for the 15 serotypes at 1 month PD3 along with the 95% CI will be calculated for V114 medium, V114 high, and the 13 serotypes in Prevnar 13TM. The one-sample two-sided CIs will be computed using the exact CI method for a single binomial proportion given in Collett [7]. Additionally, the

difference (V114 minus Prevnar 13TM) in the proportion of subjects achieving an IgG concentration $\geq 0.35\mu\text{g/mL}$ along with two-sided 95% CIs will be computed for each of V114 medium and V114 high relative to Prevnar 13TM for the 13 serotypes in common. The CI for the difference will be computed using the method of Miettinen and Nurminen [8].

The additional secondary infant immunogenicity objective (#2) as well as the secondary adult immunogenicity objective #1 will utilize similar statistical methods as those outlined above.

Reverse cumulative distribution functions for both IgG and OPA levels at PD3 and PD4 will be graphically displayed by serotype in the CSR.

Table 4 summarizes the key immunogenicity analyses.

Table 4 Analysis Strategy for Key Immunogenicity Variables

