Endpoint/Variable (Description, Time Point)	Statistical Method	Analysis Population	Missing Data Approach
Primary Objectives			
PD3 GMCs, for the 15 serotypes in V114 and the 13 serotypes in Prevnar 13™ [V114 medium, V114 high, Prevnar 13™] (Infant Primary Objective #2)	
 • Within-group GMCs and 95% CI • GMC ratio (V114 arm/Prevnar 13™) and 95% CI (2-sample t-test) for common serotypes 	Infant Per-Protocol	Missing data will be dropped
PD3 GMCs, for the 15 serotypes in V114 and the 13 serotypes in Prevnar 13™ [V114 medium, V114 high, Prevnar 13™] (Infant Primary Objective #2)	
 • Within-group GMCs and 95% CI • GMC ratio (V114 arm/Prevnar 13™) and 95% CI (2-sample t-test) for common serotypes 	Infant FAS [Supportive]	Missing data will be dropped
Secondary Objectives			
PD3, pre-dose 4, PD4 % \geq 0.35, for the 15 serotypes in V114 and the 13 serotypes in Prevnar 13™ [V114 medium, V114 high, Prevnar 13™] (Infant Secondary Objective #1)	
 • Within-group %\geq0.35 and 95% CI • Difference in %\geq0.35 (V114 arm-Prevnar 13™) and 95% CI (M&N) for common serotypes 	Infant Per-Protocol	Missing data will be dropped
Pre-dose 4 and PD4 GMCs, for the 15 serotypes in V114 and the 13 serotypes in Prevnar 13™ [V114 medium, V114 high, Prevnar 13™] (Infant Secondary Objective #2)	
 • Within-group GMCs and 95% CI • GMC ratio (V114 arm/Prevnar 13™) and 95% CI (2-sample t-test) for common serotypes 	Infant Per-Protocol	Missing data will be dropped
PD1 GMCs and fold-rises from baseline, for 15 serotypes in V114 and the 13 serotypes in Prevnar 13™ [V114 medium, V114 high] (Adult Secondary Objective #1)	
 • Within-group GMCs and 95% CI • Within-group fold-rises from baseline and 95% CI 	Adult Per-Protocol	Missing data will be dropped

The strategy to address multiplicity issues is described in Section 8.7, Interim Analyses and in Section 8.8, Multiplicity.

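### Does Table 7 overstate the trial's power by using a one-sided 5% level when the PD3 GMC ratios will be reported with two-sided 95% confidence intervals?

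*Combined protocol and SAP*

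**What the plan says.** Section 8.9 gives power for finding a lower GMC for one serotype between two vaccination groups, "assuming 45 evaluable subjects per group (90% evaluability) and a one-sided alpha of 0.05". For SD 1.0 and a true 2-fold difference it says that "between any two vaccination groups, there is >90% (94.7%) power to detect a lower response". The summary in Section 8.1 repeats the level: "a one-sided alpha of 0.05, there is >90% power to detect a lower response".

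For the primary PD3 GMCs, Table 4 in Section 8.6.1 lists "GMC ratio (V114 arm/Prevnar 13™) and 95% CI (2-sample t-test) for common serotypes" for both the per-protocol and the FAS analysis. The text of 8.6.1 confirms that the ratios come "along with two-sided 95% CIs will be computed for each of V114 medium and V114 high relative to" the control. Section 8.1 gives the method: "The CI for the ratio will be calculated using a 2-sample t-test approach based on the natural logarithm of the ratio".

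On inference, Section 8.3 states: "This is an estimation study and no formal hypothesis testing will be performed". Section 8.8 follows: "Since there are no formal hypothesis tests in this study, no adjustment will be made for multiplicity".

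**The concern.** Power is normally quoted at the level of the analysis that will be reported. A two-sided 95% interval that lies wholly below 1 corresponds to a one-sided test at 2.5%, not 5%. For the primary V114/Prevnar 13 comparison the plan has no 90% interval, one-sided bound or one-sided test, so nothing reported for it runs at Table 7's level.

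A reader who puts Table 7 beside the eventual ratio intervals might therefore expect them to exclude 1 more often than they will. If the sample size or a decision rested on that expectation, the design would be somewhat weaker than it appears. The footnote to Table 7 describes its SDs as representative of V114-003, so the rows with larger SDs are not remote scenarios.

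**Working it through.** **Inputs (Section 8.9).** There are 45 evaluable infants per group; the SD of the natural-log concentration is 0.8 to 1.4; the true fold difference is 1.5, 2.0 or 2.5; alpha is one-sided 0.05. Section 8.6.1 specifies a two-sample t approach on the log scale.

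**Formula.** Power = P(T > t(1 − α, 88)), where T is noncentral t with 45 + 45 − 2 = 88 degrees of freedom and noncentrality ln(fold) / (SD × √(2/45)).

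**The plan's own figure.** At SD 1.0 and 2-fold, the noncentrality is 0.693 / (1.0 × 0.2108) = 3.29. At one-sided 0.05 this gives 94.71%, which matches the stated 94.7%. The other 11 cells also reproduce, to about 0.1 point.

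**The alternative reading.** Suppose, as an assumption, that a lower response counts as detected when the two-sided 95% interval lies wholly below 1. That is one-sided 0.025 in the same formula. Table 7's value comes first in each cell, the alternative second:

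| SD | 1.5-fold | 2.0-fold | 2.5-fold |
|---|---|---|---|
| 0.8 | 77.1 / 66.2% | 99.3 / 98.2% | >99 / >99% |
| 1.0 | 60.4 / 47.7% | 94.7 / 90.2% | 99.6 / 99.0% |
| 1.2 | 47.8 / 35.4% | 85.9 / 77.3% | 97.4 / 94.8% |
| 1.4 | 38.9 / 27.4% | 75.3 / 64.2% | 92.4 / 86.7% |

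The largest drop is 60.4 − 47.7 = 12.7 points, at SD 1.0 and 1.5-fold. For the one scenario about which the text makes a claim, the drop is 94.7 − 90.2 = 4.5 points, and the result stays above 90%.

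**Does the plan use the alternative rule?** No.

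- Sections 3.1, 8.3 and 8.8 all exclude formal hypothesis testing, and no section attaches a conclusion to a GMC-ratio interval that excludes 1.
- Section 8.7 says that neither interim analysis alters the conduct of the study.
- Section 8.9 gives about 250 infants and then describes what 45 evaluable per arm would provide. It does not solve for a sample size from a target power.
- Section 8.9 words Table 7 for any two vaccination groups, and exploratory objective 3 (Section 3.3) compares the V114 formulations with one another. Section 8.6.1 leaves exploratory methods to the supplemental SAP. The table is therefore a general planning display, not one tied only to the Prevnar 13 ratio.

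**Precision of the ratio.** The expected 95% interval is the estimate divided and multiplied by exp(t(0.975, 88) × SD × √(2/45)). The factors are 1.40, 1.52, 1.65 and 1.80 at SD 0.8, 1.0, 1.2 and 1.4. At SD 1.0, an observed ratio of 0.50 would have limits 0.50 / 1.52 = 0.33 and 0.50 × 1.52 = 0.76.

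These follow from the stated SD and group size. Table 8 nearly gives them already: its factor at SD 1.0 is 1.35 for a single group, and two equal groups widen the log half-width by √2, so exp(√2 × ln 1.35) = 1.53. The small difference from 1.52 comes from rounding and from the different degrees of freedom.

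**The case for a change.** The strongest argument on the other side needs no detection rule. In an estimation study the natural design quantity is the expected precision of what is estimated. Primary objective 2 names the GMC ratios, yet Table 8 shows intervals for single-group GMCs only. The sole between-group design figures are powers at a level that the primary ratio output does not use, and Section 8.9 speaks of detection without defining it. Under the interval reading some cells move noticeably: at 2-fold, from 85.9% to 77.3% with SD 1.2 and from 75.3% to 64.2% with SD 1.4. The interim results are also meant to inform later studies, so readers might want to know how wide the ratio intervals will be.

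The facts in this stand: the levels differ, detection is undefined, and ratio precision is not tabulated. They do not add up to a defect. The one-sided level is printed in both places where power is claimed, so a reader is misled only by passing over it. A planning alpha in an estimation study need not be the complement of the reporting confidence level. Anyone who wants the ratio's precision can obtain it from the stated SD and n, as shown in the working.

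**Conclusion.** The concern does not hold. Table 7 is arithmetically correct at its disclosed level, and the design delivers the power it states. The contrast of 94.7% with 90.2% arises only under a criterion that the plan does not contain, and the claim of more than 90% holds under either reading, though narrowly under the second. The drops of up to 12.7 points lie in cells for which the text claims no adequacy; in the cell with the largest drop, Table 7 itself shows only 60.4%.

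Following the plan as written gives the same sample size, analyses and results whichever level the table uses. The calculations assume 45 evaluable infants per arm, a common SD within the tabulated range and the two-sample t approach on the log scale. The conclusion would change only if the plan attached a decision to a ratio interval excluding 1, and for the GMC comparisons it attaches none.

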8.10 Subgroup Analyses and Effect of Baseline Factors

No analyses for these factors will be performed.

8.11 Extent of Exposure

The number of subjects vaccinated at each vaccination visit will be summarized by vaccination group.

9.0 LABELING, PACKAGING, STORAGE AND RETURN OF CLINICAL SUPPLIES

9.1 Investigational Product

The investigator shall take responsibility for and shall take all steps to maintain appropriate records and ensure appropriate supply, storage, handling, distribution and usage of investigational product in accordance with the protocol and any applicable laws and regulations.

Clinical Supplies will be provided by the Sponsor as summarized in [Table 9](#).

Clinical supplies will be packaged to support enrollment as required.

Table 9 Product Descriptions

Product Name & Potency	Dosage Form
V114 medium	0.5 mL dose sterile suspension for I.M. injection
V114 high	0.5 mL dose sterile suspension for I.M. injection
V114 medium with an alternative carrier protein	0.5 mL dose sterile suspension for I.M. injection
V114 high with an alternative carrier protein	0.5 mL dose sterile suspension for I.M. injection
Prevnar 13™	0.5 mL dose sterile suspension for I.M. injection

9.2 Packaging and Labeling Information

Clinical supplies will be affixed with a clinical label in accordance with regulatory requirements.

Sites will receive open label, single dose syringe kits. Each kit will contain 1 syringe.

9.3 Clinical Supplies Disclosure

This trial is blinded but provided open label; therefore, an unblinded pharmacist or qualified trial site personnel will be used to blind supplies. Vaccine identity (name, strength or potency) is included in the label text; random code/disclosure envelopes or lists are provided.

The emergency unblinding call center will use the randomization schedule for the trial to unblind subjects and to unmask vaccine identity. In the event that the emergency unblinding call center is not available for a given site in this trial, the central electronic randomization system (IVRS/IWRS) should be used in order to unblind subjects and to unmask

treatment/vaccine identity. The Sponsor will not provide random code/disclosure envelopes or lists with the clinical supplies.

Vaccine identification information is to be unmasked ONLY if necessary for the welfare of the subject. Every effort should be made not to unblind the subject unless necessary.

In the event that unblinding has occurred, the circumstances around the unblinding (e.g., date and reason) must be documented promptly, and the Sponsor Clinical Director notified as soon as possible. Only the principal investigator or delegate and the respective subject's code should be unblinded. Trial site personnel and Sponsor personnel directly associated with the conduct of the trial should not be unblinded.

9.4 Storage and Handling Requirements

Clinical supplies must be stored in a secure, limited-access location under the storage conditions specified on the label.

Receipt and dispensing of trial medication must be recorded by an authorized person at the trial site.

Clinical supplies may not be used for any purpose other than that stated in the protocol.

9.5 Discard/Destruction>Returns and Reconciliation

The investigator is responsible for keeping accurate records of the clinical supplies received from the Sponsor or designee, the amount dispensed to and returned by the subjects and the amount remaining at the conclusion of the trial. For all trial sites, the local country Sponsor personnel or designee will provide appropriate documentation that must be completed for drug accountability and return, or local discard and destruction if appropriate. Where local discard and destruction is appropriate, the investigator is responsible for ensuring that a local discard/destruction procedure is documented.

9.6 Standard Policies

Trial site personnel will have access to a central electronic randomization system (IVRS/IWRS system) to allocate subjects, to assign vaccine to subjects and to manage the distribution of clinical supplies. Each person accessing the IVRS system must be assigned an individual unique PIN. They must use only their assigned PIN to access the system, and they must not share their assigned PIN with anyone.

10.0 ADMINISTRATIVE AND REGULATORY DETAILS

10.1 Confidentiality

10.1.1 Confidentiality of Data

By signing this protocol, the investigator affirms to the Sponsor that information furnished to the investigator by the Sponsor will be maintained in confidence, and such information will

be divulged to the institutional review board, ethics review committee (IRB/ERC) or similar or expert committee; affiliated institution and employees, only under an appropriate understanding of confidentiality with such board or committee, affiliated institution and employees. Data generated by this trial will be considered confidential by the investigator, except to the extent that it is included in a publication as provided in the Publications section of this protocol.

10.1.2 Confidentiality of Subject Records

By signing this protocol, the investigator agrees that the Sponsor (or Sponsor representative), IRB/ERC, or regulatory authority representatives may consult and/or copy trial documents in order to verify worksheet/case report form data. By signing the consent form, the subject agrees to this process. If trial documents will be photocopied during the process of verifying worksheet/case report form information, the subject will be identified by unique code only; full names/initials will be masked prior to transmission to the Sponsor.

By signing this protocol, the investigator agrees to treat all subject data used and disclosed in connection with this trial in accordance with all applicable privacy laws, rules and regulations.

10.1.3 Confidentiality of Investigator Information

By signing this protocol, the investigator recognizes that certain personal identifying information with respect to the investigator, and all subinvestigators and trial site personnel, may be used and disclosed for trial management purposes, as part of a regulatory submissions, and as required by law. This information may include:

1. name, address, telephone number and e-mail address;
2. hospital or clinic address and telephone number;
3. curriculum vitae or other summary of qualifications and credentials; and
4. other professional documentation.

Consistent with the purposes described above, this information may be transmitted to the Sponsor, and subsidiaries, affiliates and agents of the Sponsor, in your country and other countries, including countries that do not have laws protecting such information. Additionally, the investigator's name and business contact information may be included when reporting certain serious adverse events to regulatory authorities or to other investigators. By signing this protocol, the investigator expressly consents to these uses and disclosures.

If this is a multicenter trial, in order to facilitate contact between investigators, the Sponsor may share an investigator's name and contact information with other participating investigators upon request.

